9.2.2.3 Secondary Objective Assessments

The secondary objectives of this observational study are to:

- Collect data on pregnancy, birth and maternal complications in case of pregnancies exposed to ella®.
- In addition to statistical analysis, pregnancy, birth and maternal complications will be described with a case by case approach, and the relationship with ella® intake (certain / probable / possible / unlikely / not related / unknown) will be assessed by pregnancy data monitoring board (DMB).
- Assess the nature and incidence of complications of pregnancy loss in pregnancies exposed to ella®.

Complications of pregnancy loss are of special interest, in particular excessive and prolonged bleeding events.

Duration of bleeding events will be described in terms of descriptive statistics (mean, standard deviation, median, range).

The cumulative incidence of excessive bleeding episodes (considered as excessive by the HCP) will be calculated by dividing their occurrence by the number of pregnancy losses during the study.

Cumulative incidence of maternal health complications related to pregnancy loss will also be calculated by dividing the number of complications by the number of pregnancy losses.

These proportions (cumulative incidence) of adverse events and their 95% confidence intervals will be calculated for the overall sample as well as by country, in order to assess potential differences due to variations in clinical practice regarding the management of pregnancies and pregnancy complications. Results will also be presented by age.

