4 SELECTION OF WOMEN

4.1 Number of women

As per rationale detailed in section 9.1, a total of 400 ella®-exposed pregnancies with known outcomes will be analysed.

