11 DATA MONITORING BOARD

An independent board of experts will evaluate outcomes of exposed pregnancies reported to the Sponsor's Pharmacovigilance department. All pregnancies entered in the pharmacovigilance database (all clinical studies, European registry, spontaneous pharmacovigilance reporting) will be reviewed and assessed by the board. It is a multidisciplinary and multinational board including the following medical specialties:

- 1 Obstetrics–Gynaecology/Reproductive Endocrinology specialist;
- 1 Dysmorphologist specialized in congenital anomalies;
- 1 Paediatrician specialized in neonatology;
- 1 Statistician with a sub-specialty in epidemiology.

This group will serve as an autonomous independent pregnancy Data Monitoring Board (DMB) reviewing all reported pregnancies from all sources (all past and current clinical trials including the ellipse II study, European registry and spontaneous pharmacovigilance case reports) periodically reviewing the reported outcomes of all pregnancies exposed to ella® by batches of 50. Moreover if specific safety issues are detected, a DMB meeting may be called by HRA Pharma.

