11.1 Assessment of pregnancy outcome

According to the following information provided (date of last menstrual period, date of ella® intake, associated risks factors), the DMB will review all pregnancy outcomes and determine for each pregnancy complication whether it could be linked to ella® intake.

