11.2 DMB assessment

Following data review, the DMB will prepare a synopsis report stating that it performed a review and giving conclusions as follows:

Conclusions on the case evaluated:

1. *There is no relationship between ella® intake and the outcome observed.*

2. *The relationship between ella® intake and the outcome observed is unknown.*
3. *It is unlikely that the outcome reported is due to ella® intake.*
4. *It is possible that the outcome reported is due to ella® intake.*

For any of the conclusions, the DMB chair will provide a copy of the written synopsis including the conclusions made during the meetings as well as supplementary comments as applicable to HRA Pharma within 15 days after the DMB meeting.

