11.3 DMB working procedures

Prior to the first review, the sponsor will provide the DMB with written standard operating procedures describing the list of members, their CVs, the frequency of review, the list of data to be reviewed, the list of conclusions applicable to evaluated cases and the list of records to be archived.

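### The data monitoring board has two causality scales, six grades in section 9.2.2.3 and four in section 11.2, and the shorter one stops at 'possible'

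*Protocol*

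**What the plan says.** Section 9.2.2.3 of the protocol, on the secondary objectives, provides for individual review: "pregnancy, birth and maternal complications will be described with a case by case approach, and the relationship with ella® intake" is to be judged on a stated scale by a stated assessor, "certain / probable / possible / unlikely / not related / unknown) will be assessed by pregnancy data monitoring board (DMB". That is six grades.

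Section 11.1 gives the board its task for each case, which is to "determine for each pregnancy complication whether it could be linked to" intake of the drug. Section 11.2 then lists the conclusions the board may give on a case. There are four, and the last and strongest begins "It is possible that the outcome reported is due to". The other three are no relationship, relationship unknown, and unlikely. For any of these, "the DMB chair will provide a copy of the written synopsis including the conclusions made during the meetings" to the sponsor, with supplementary comments where applicable.

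Section 11.3 says that the sponsor's written operating procedures for the board will include "the list of conclusions applicable to evaluated cases". It does not say which list that is.

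**The concern.** One board, judging the same kind of case, is given two scales of different length. Both leave room for uncertainty and for a weak link, but only the scale in section 9.2.2.3 has room for a strong one.

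At stake is the independent expert judgement on individual cases. If the board works from section 11.2, a case it considers probably or certainly due to the drug has to be recorded as 'possible', alongside cases where the link is merely conceivable. The loss runs one way, towards understatement. The six-level grading promised in section 9.2.2.3 could then not be recovered from the synopsis conclusions, because 'possible' would hold up to three different grades.

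**Working it through.** No power, sample size or error rate is involved. The check is to match the categories, confirm that both lists apply to the same cases, and look for text that reconciles them.

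**Step 1. Match the categories.**

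| Section 9.2.2.3 (board's grade) | Section 11.2 (board's conclusion) |
|---|---|
| certain | none |
| probable | none |
| possible | conclusion 4, possible |
| unlikely | conclusion 3, unlikely |
| not related | conclusion 1, no relationship |
| unknown | conclusion 2, unknown |

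Six grades less four matched leaves 6 − 4 = 2 without a counterpart. Both lie above 'possible'. The list in section 11.2 is numbered 1 to 4 and the text runs straight on to what happens for any of the conclusions, so there is no sign that an item was lost from the document.

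**Step 2. Same assessor, same cases?** Both sections name the data monitoring board. Section 9.2.2.3 speaks of complications and section 11.2 of the outcome, which might suggest two separate exercises. Section 11.1 rules that out: it has the board decide on each pregnancy complication, and section 11.2 is where the results of that review are reported.

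**Step 3. Is there a reconciling rule?** None was found. No section maps one list to the other, gives them different purposes or ranks them. Section 11.3 only promises a list. If the procedures adopt four levels they depart from section 9.2.2.3; if they adopt six they depart from section 11.2.

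**Step 4. How often would the cap apply?** Section 11 describes the board as "periodically reviewing the reported outcomes of all pregnancies exposed to ella® by batches of 50". Section 4.1 states that "a total of 400 ella®-exposed pregnancies with known outcomes will be analysed". If all 400 pass through the board in full batches, that is 400 / 50 = 8 reviews, each with its synopsis. This counts occasions, not affected cases. The board also sees pregnancies from other studies, the European registry and spontaneous reports, and the sponsor may call extra meetings, so the actual number may differ.

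**Step 5. What uses the grade?** The proportions in section 9.2.2.2, the incidences of excessive bleeding and of complications of pregnancy loss in section 9.2.2.3, and the tests and models in section 9.2.2.4 are defined from event counts, denominators and measurements. None refers to the causality grade.

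**The case against.** The strongest reply is that little depends on the mismatch.

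- **Nothing hangs on the top two grades.** No action, threshold or analysis is tied to probable or certain. Section 10 lists expedited reports mainly by type of event, and none is stated to wait for a board grade. This stands, and it limits the weight of the point.
- **There are other causality assessments.** Section 8.1 has the health care professional and the standard pharmacovigilance process assess the relationship in all cases, and the synopsis also assigns it to pharmacovigilance. So the board's synopsis is not the only record, and a strong link need not go unnoticed. That is a real safeguard, but it does not replace the independent judgement that section 9.2.2.3 asks of the board.
- **The lists are nested.** Section 11.1 asks only whether a complication could be linked to intake, and 'possible' answers yes. Section 11.2 might then be a coarse summary with the finer grade held elsewhere. The protocol does not say so, and it names no other place where the board would record the finer grade.
- **The procedures or the comments may fill the gap.** The procedures are not shown and may settle the working list, but they cannot agree with both sections as they stand. Comments are provided only where applicable, and free text is not a grade that can be tabulated.
- **The figure of 8 reviews does not measure impact.** Agreed. It shows only that the cap would recur.

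These points reduce the consequence. They do not remove the contradiction.

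**Conclusion.** The concern holds. Sections 9.2.2.3 and 11.2 give the same board two scales for the same cases. They agree on four levels and conflict on two, probable and certain. If section 11.2 governs, the board's formal conclusion is capped at 'possible' at every review, and any error is towards understating the link.

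This rests on reading section 11.2 as the complete list of allowed conclusions, which is how it is written. The number of cases affected cannot be given, because the documents offer no expected share of probable or certain cases. The damage is confined to the board's case-level causality record and what is drawn from it. No estimate, interval or test changes. It should be corrected, but it does not threaten the primary objective.

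**What to change.** Use one list throughout. The simplest way is to add probable and certain to the conclusions in section 11.2, so that they match the six grades in section 9.2.2.3, and to put that same list into the operating procedures under section 11.3. Cutting section 9.2.2.3 down to four levels would also remove the contradiction, but it would discard the distinction that matters most for a strong signal. Extending section 11.2 loses nothing.

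The cost is a wording change in section 11.2 and in the procedures. If the board has already graded cases on the four-level list, it should re-grade those rated 'possible', since that is where a stronger judgement would have been recorded. The other ratings can stay.

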4.2.2 Completion of the Woman on-line questionnaires by the woman

There will be one online questionnaires to be completed by women, which will be different from that for HCPs.

A single questionnaire will be completed by the woman, where data on pregnancy diagnosis, exposure to ella®, and if known at the time of the questionnaire completion, the pregnancy outcome. If not known at the time of the first completion, the woman will have the option to get back to the questionnaire and continue its completion when the outcome will be known.

For live birth, woman will also be requested to complete a follow-up questionnaire 4 months after the delivery date (**4-month Follow-Up Woman Form**).

The language of the woman questionnaire will be further adapted to facilitate understanding and format will have functional ergonomics that are permitted by online data entry such as linked questions, drop-down menus, and agenda for fill in dates. In addition, some of the questions will integrate a specific tutorial for helping the declarant to enter appropriate answers. Contents of the information requested in the woman questionnaires are detailed in a specific distinct document submitted to the IRB for its approval prior to implementation.

Women who do not want to provide their HCP contact details, will have the option to contact a referent physician who will be commissioned to follow-up directly with the women. Referent physician will be able to answer their questions and guide them through the questionnaire completion process. The referent physician will not be able to complete the woman questionnaire on their behalf.

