8 STUDY PROCEDURES AND SCHEDULE

8.1 Overview of safety data

Pregnancy information

Date of diagnosis, date of LMP, date and results of ultrasound (if applicable) and expected delivery date.

Exposure to ella®

Data on exposure to ella® include date of ella® intake and number of tablets taken, time from intercourse to ella® intake; pregnancy stage at ella® exposure, pregnancy status before ella® intake.

Outcomes

All outcomes and the data collected to assess them are:

- Live birth – gender, birth weight, gestational age, delivery method and Apgar scores will be collected in all cases. For healthy babies and those with congenital anomalies or other neonatal diagnosis, the study observation period will last until 4 months after delivery;
 - Congenital anomaly or other neonatal diagnosis – description of anomaly and possible causes will be additionally collected;
 - Neonatal death (from birth through to 28 completed days of age*) – age at death, possible etiology and result of autopsy if performed will be additionally collected.
- Pregnancy loss – gestational age, possible etiology of pregnancy loss and any complications (vaginal bleeding, need for curettage, infection) will be collected in all cases.
 - Spontaneous abortion (or early fetal death i.e. < 20 completed weeks of gestation*)
 - Ectopic pregnancy
 - Induced abortion (no medical reason – woman's elective choice, elective abortion with fetal defects, or maternal health complications)
 - Stillbirth:
 - Intermediate fetal death (more than 20 completed weeks of gestation but less than 28*)
 - Late fetal death (\geq 28 completed weeks of gestation*).

Maternal health complications of pregnancy

In all cases, relationship of the outcome observed with the exposure to ella® will be assessed by the HCP and according to the standard pharmacovigilance process.

* According to the WHO International Classification of Disease (ICD)

Prior and concomitant medications

Prior and concomitant medications will be collected in the HCP or women questionnaires. Collection period covers the pregnancy duration from LMP to the end of pregnancy.

Other

Maternal family history; recreational drug use (tobacco, alcohol, illicit drugs) and serological and prenatal tests.

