8.2.1.3 Completion of the Pregnancy Outcome Forms

When the outcome of the pregnancy is known*, the HCP will be asked to fill-in the Pregnancy Outcome forms.

- Access the website with the HCP unique user ID and password
- Start the Pregnancy Outcome Form completion
- Collect the pregnancy outcome observed [live birth (i.e. healthy baby, congenital anomaly, neonatal death) including pregnancy complications, pregnancy loss (including spontaneous abortion, ectopic pregnancy, therapeutic abortion, intermediate or late fetal death), maternal health complications]
- Collect recreational drug use (tobacco, alcohol, illicit drugs), if any
- Collect relevant maternal and family medical history, including history related to previous pregnancies, including congenital birth defects
- Collect serology and prenatal tests (type, date, results)
- Collect relevant concomitant medications
- Save and submit the forms.

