8.2.1.4 Completion of the 4-month Follow-Up HCP Forms

In case of live birth and 4 months after the delivery, the HCP be reminded to re-access the website. The HCP will be asked to:

- Access the website with the HCP unique user ID and password
- Collect the age, height and weight of the baby
- Collect congenital anomaly detected since birth, if applicable
- Collect late development detected since birth, if applicable
- Collect death data, if applicable.

8.2.2 Completion of the on-line questionnaire directly by the woman:

Up to three questionnaires will be completed by the woman: the first two ones including Pregnancy and Outcome Forms, and one for live birth only, a 4-month Follow-up Form.

* In case a woman completed the questionnaire on her own, she should be reminded to bring her unique patient number to allow the HCP to provide further information on the pregnancy if requested.

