8.2.2.2 Completion of the Pregnancy and Outcome Forms

- Access the on-line questionnaire
- Provide first 3 characters of her last name and first character of her first name, date of birth, e-mail address (which will be blinded to the sponsor), her weight and height
- Provide information on pregnancy [including date of diagnosis, date of LMP, date and results of ultrasound (if applicable), expected delivery date]
- Provide data on ella® exposure (date of ella® intake, number of tablets taken, time from unprotected intercourse to ella® intake, pregnancy stage at exposure, additional ella® intake)
- Provide relevant concomitant medications taken during the pregnancy, including hormonal contraception or folic acid at the time of conception
- Report any relevant medical condition preceding or during pregnancy (e.g. diabetes, hypertension)
- Provide the pregnancy outcome observed [live birth (including healthy baby, congenital anomaly, neonatal death), pregnancy loss (including spontaneous abortion, ectopic pregnancy, therapeutic abortion, intermediate or late fetal death)]
- Provide recreational drug use (tobacco, alcohol, illicit drugs), if any
- Provide HCP details*. If the woman is not willing to provide her HCP details, she will be invited to contact a referent physician for assistance in the completion of the questionnaire
- Save and submit the questionnaire
- A unique patient number will be sent by e-mail to the woman, to be used for further access to the website. The woman will be able to further access her file at any time by using her unique patient number and continue the questionnaire completion when additional follow-up data is known.

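### The excessive-bleeding rate needs an HCP judgement in the numerator but not in the denominator, so losses with no HCP input count as non-events

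*Protocol*

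**What the plan says.** Protocol section 9.2.2.3 gives this endpoint weight: "Complications of pregnancy loss are of special interest, in particular excessive and prolonged bleeding events". It then fixes the calculation: "excessive bleeding episodes (considered as excessive by the HCP) will be calculated by dividing their occurrence by the number of pregnancy losses during the study". It does not require that an HCP assessed the loss, and it gives no rule for losses that no HCP assessed. The next sentence of the section divides maternal complications of loss by the same denominator, but without the HCP condition.

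Data arrive by two routes.

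- **HCP route.** The outcome list in 8.2.1.3 ends with "intermediate or late fetal death), maternal health complications".
- **Woman's route.** The list in 8.2.2.2 asks for "pregnancy loss (including spontaneous abortion, ectopic pregnancy, therapeutic abortion, intermediate or late fetal death" and names no complication of loss. Its nearest item is "Report any relevant medical condition preceding or during pregnancy (e.g. diabetes, hypertension".

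Section 8.1, which covers both routes, says of pregnancy loss that "any complications (vaginal bleeding, need for curettage, infection) will be collected in all cases". Section 4.2.2 adds: "Contents of the information requested in the woman questionnaires are detailed in a specific distinct document submitted to the IRB".

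A woman may decline to name her HCP (4.2.2, 8.2.2.2). Requests for further information then go to her by e-mail (8.3), and the referent physician who helps her may not fill in her form (4.2.2). Where she does name an HCP, a footnote to the HCP forms has her bring her patient number "to allow the HCP to provide further information on the pregnancy if requested".

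**The concern.** A proportion is interpretable only if every unit in the denominator could have been recorded as an event. Here a loss reported by the woman alone, with no HCP input, cannot meet the numerator's criterion as written, yet it adds one to the denominator. Not assessed is read as not affected.

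This concerns a safety rate under a stated secondary objective. An understated rate also brings a confidence interval that is too low and, because unassessed losses are counted as information, too narrow. Such losses are plausible: the introduction reports that the US clinics using the product mostly lose contact with women once they are pregnant.

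**Working it through.** The protocol states no expected incidence of excessive bleeding, no expected number of losses and no split by reporter. There is no planned figure to reproduce, and everything numerical below rests on assumed values.

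**Step 1. Can a loss lack an HCP judgement?** Yes. Sections 4.2.2, 8.2.2.2 and 8.3 together allow a complete self-report with no HCP named, follow-up through the woman only, and no physician entry on her form. The scheduled contacts at 20 weeks and at the delivery date in 8.3 are for HCPs who enrolled a woman.

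**Step 2. Effect on the rate.** Let

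- p = true incidence per loss (assumed 5%, 10% or 20%);
- f = share of losses with no HCP form (assumed 10% to 75%);
- s = share of events among those losses that still obtain an HCP judgement (0 = none, 1 = all).

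Expected rate as written = p × [(1 − f) + f × s].

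| f | p = 5%, s = 0 | p = 10%, s = 0 | p = 20%, s = 0 | p = 10%, s = 0.5 |
|---|---|---|---|---|
| 10% | 4.5% | 9.0% | 18% | 9.5% |
| 25% | 3.75% | 7.5% | 15% | 8.75% |
| 50% | 2.5% | 5.0% | 10% | 7.5% |
| 75% | 1.25% | 2.5% | 5% | 6.25% |

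For example, 10% × (1 − 0.25) = 7.5%. With s = 0 the relative understatement equals f; with s = 1 it is zero.

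**Step 3. Effect on the interval.** Take 80 losses (assumed, 20% of the planned 400 pregnancies), p = 10%, s = 0, and exact 95% intervals.

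| f | As written | HCP-assessed losses only |
|---|---|---|
| 25% | 6/80 = 7.5% (2.8 to 15.6) | 6/60 = 10.0% (3.8 to 20.5) |
| 50% | 4/80 = 5.0% (1.4 to 12.3) | 4/40 = 10.0% (2.8 to 23.7) |
| 75% | 2/80 = 2.5% (0.3 to 8.7) | 2/20 = 10.0% (1.2 to 31.7) |

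**Step 4. If HCP assessment is related to bleeding.** Steps 2 and 3 assume equal incidence in assessed and unassessed losses. Let these be a and u instead, with s = 0.

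- True rate = (1 − f) × a + f × u.
- As written = (1 − f) × a, which is too low by f × u.
- Assessed only = a, which is off by f × (a − u).

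With f = 50%, a = 20% and u = 5%: true = 10% + 2.5% = 12.5%; as written = 10%; assessed only = 20%. So, among the losses in the dataset, the written rate is a lower bound if each loss is counted once. The assessed-only rate is too high whenever assessed losses bleed more.

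**Step 5. Precedent in the protocol.** Section 9.2.2.2 already divides normal-appearing pregnancies before induced abortion by only those whose ultrasound could be analysed. That is the assessed-only logic missing here.

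**The case against.** Several objections have force.

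- **Not all self-enrolled women are affected.** A reader might infer that no self-reported loss can be an event. The documents do not support that. Women are asked for HCP details, an HCP may add information, and the sponsor may contact reporters, mainly HCPs (8.3). A woman might also relay her clinician's opinion. Only losses with no HCP judgement by any path are affected.
- **The form may be complete.** A reader might infer that the woman's questionnaire omits bleeding, curettage and infection. But 8.2.2.2 is a summary, and the full content is in a separate document not at hand. The summary also omits birth weight and Apgar scores, which 8.1 collects for every live birth. The study schedule marks maternal and fetal complications at three time points without distinguishing the reporter. What stands is an unreconciled difference between 8.1 and 8.2.2.2.
- **Maternal complications of loss.** That rate carries no HCP condition. It shares the problem only where the item was not collected.
- **Size and net direction are unknown.** Both f and p are assumed. Women with complicated losses may report more often, and the numerator counts episodes rather than women; either could raise the figure. Section 9.2.1 pools other sources, and if the bleeding rate uses that pool, f could differ greatly.
- **The remedy has its own bias**, as Step 4 shows.
- **The rate is descriptive.** No decision rule depends on it, and the data monitoring board reviews every reported pregnancy.

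None of this removes the mismatch. Even if the woman's form asks about bleeding, her own answer is not an HCP judgement. Nor is it a detail left to the SAP, because the protocol itself fixes the ratio.

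**Conclusion.** The point holds in a limited form. As written, losses with no HCP judgement count as losses without excessive bleeding. Other things equal, the rate is understated by their share of all losses. That statement assumes similar bleeding incidence in assessed and unassessed losses, and that no judgement reaches the sponsor for the latter.

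The protocol does not allow the size to be determined: it is nil if every loss obtains an HCP judgement, and a halving if half do not. A firm claim that the reported figure will lie below the truth would go too far, because over-reporting of complicated losses could act the other way. This is a correction worth making to a secondary safety rate; it does not affect the primary objective.

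**What to change.** 1. In 9.2.2.3, make the denominator for excessive bleeding the pregnancy losses with an HCP bleeding assessment, and report the number of losses without one.
2. Show the all-losses rate beside it as a lower-bound sensitivity figure, counting each loss at most once so that the bound holds.
3. Tabulate woman-reported bleeding separately from HCP-judged bleeding.
4. For maternal complications of loss, use an assessed-only denominator only where the item was not collected.
5. Reconcile 8.2.2.2 with 8.1 by confirming that the woman's questionnaire contains the loss-complication items, and amend whichever text is wrong.

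The cost is a few sentences in the protocol and, if the items prove absent, a few questions on the web form. The statistical price is a smaller denominator and a wider interval (in the illustration at f = 50%, 2.8 to 23.7% instead of 1.4 to 12.3%). The assessed-only rate may also overstate incidence if HCPs see the more complicated losses, which is why both rates should be shown.
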